PICC	Peripherally inserted central catheter

Study Aim

Currently there is little international or UK consensus regarding the route or duration of antibiotic treatment for acute osteomyelitis (OM)/septic arthritis (SA) in children. Data regarding paediatric bone and joint infections in the UK are scarce and outdated. This service evaluation will be used to:

1. Assess current case load, disease spectrum & clinical practice in the diagnosis & treatment of OM/SA in secondary & tertiary UK care
2. Determine whether a randomised controlled trial to investigate shorter duration of intravenous antibiotic therapy for bone and joint infections in children is feasible in the future.

This will be achieved in conjunction with a future component of the study (analysis plan of which not included in this document) obtaining qualitative & quantitative data on:

- a) willingness of clinicians to randomise to proposed protocol
- b) willingness of patients & parents to be randomized
- c) number of patients seen;
- d) clinical stakeholder & consumer perception of relevant outcomes

Study Design

This service evaluation is a descriptive study, examining routinely collected clinical data for all eligible paediatric cases of OM and SA presenting at participating tertiary and secondary healthcare centres over a minimum of a 6 months period.

Participating centres

All Tertiary and Secondary centres routinely treating cases of OM or SA from across England will be invited to participate in this national service evaluation. They will record data on all cases accrued over at least a 6 month period.

Participant selection criteria

All eligible patients presenting to participating centres with a diagnosis of bone and joint infection will be enrolled with no maximum, and data will be entered into a web based database.

Inclusion Criteria

All children from birth to 16 years with a clinical diagnosis of osteomyelitis or septic arthritis admitted to participating hospitals from home, or referred from another centre.

Exclusion Criteria

Patients whose parents have specifically requested for their child not to be included in the study.

Participant identification and recruitment

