Posters displayed on admitting wards notify parents and patients that the centre is participating in a national service evaluation of children's bone and joint infections. Parents will have the opportunity to inform a member of their child's care team if they do not want their child's information entered into the database.

Sample size calculations

The study is funded to enable a maximum of 1,000 cases of OM or SA to be entered into the database. In order to get an accurate national evaluation, all participating centres will be asked to record cases for at least six months. It is estimated that at least 500 cases will be accrued by around 50 centres over a 6-12 month period. All eligible cases at participating centres will be recorded.

Data Collection

We will record demographic details and details of hospitalisation(s) including transfers between hospitals; type and site of disease; routine haematology, biochemistry and microbiology; radiological procedures; surgical procedures; length of IV therapy; antimicrobials used, route and duration; reason/criteria; used for oral switch (if any); and clinical outcomes at 3 months.

These data are to be collected from the patients' clinical notes. Training will be provided for teams at participating centres. The study will use a password protected web based data collection form that can be accessed at all participating hospitals.

Study Objectives

The study has three major objectives:

1. What are the clinical, biochemical and radiological criteria used by UK paediatricians / orthopaedic surgeons / radiologists to diagnose osteomyelitis?
2. What is the range of durations of intravenous and oral antibiotics used to treat osteomyelitis? What factors affect durations (e.g. surgery / blood tests / microbiology results).
3. What are the rates of treatment failures / complications for different:
 - (a) Antibiotic regimes used at participating centres?
 - (b) Surgery types used at participating centres?

and what actions were taken following a complication at participating centres?

These objectives are broken down into further sub-objectives:

- 1A:** Describe the study sample: demographics; past medical history; presenting limbs/joints affected; and diagnosis types aiming to identify factors predisposing children to bone and joint infections. Describe pre-presentation variables that affect drug choice, dosage and duration, in particular age, allergies and co-morbidities.

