- 1B:** Describe the clinical time-line for diagnosis: summarising the number of days from presentation when key clinical actions (1st imaging, surgery and initiation of IV antibiotics) occur.
- 1C:** Describe the surgical procedures carried out prior to diagnosis.
- 1D:** Summarise the types of microbiological tests carried out and the types of samples taken. Specifically, find the proportion of centres that are performing PCR tests, and testing for Panton-Valentine Leukocidin producing *Staphylococcus aureus*.
Calculate the proportion of children testing positive for: at least one micro-organism; and each specific micro-organism (using conventional techniques, ie not PCR).
- 1E:** Describe the combinations of blood-tests carried out at presentation and summarise the test results. Find the proportion of children with elevated results for each blood-test type at presentation (results above centre-specific normal ranges), and the proportion of children with CRP_{max} occurring at presentation. Describe the types of samples.
- 1F:** Summarise CRP_{max} by age-group and micro-organisms detected.
- 1G:** Describe the imaging methods routinely used to aid diagnosis. What proportions of each method gave an abnormal result..
- 2A:** Describe the clinical time-line for antibiotic treatment (specifically when antibiotics are started) Describe the types of antibiotic regimes prescribed. Summarise the number of different antibiotics given as initial treatment, and the total number of different antibiotics patients receive over the durations of treatment by each route. Summarise the numbers of children being given different types of regime: early vs

normal length of time to oral switch; dosage – how many were given normal doses throughout; shortened vs standard length of time on antibiotics.

- 2B:** Describe the IV and oral antibiotics prescribed during hospital stay. For each antibiotic: which were prescribed at least once; which were part of the initial treatment; what was the average daily dose; with what frequency were doses given; and was the duration greater than 1 week. Were there differences in initial IV antibiotic prescriptions between secondary and tertiary site types; between children with and without penicillin allergy; and with and without sickle cell disease?

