- Length of time on IV antibiotics
- Length of time on oral antibiotics
- Total length of time on antibiotics
- Length of time from presentation to discharge
- Blood tests carried out and their results
- Antibiotics prescribed (during hospital stay and at discharge)
- Dosage (Normal / High as defined in Children's British National Formulary)
- Adherence to discharge prescription
- Reasons for non-adherence or changes to prescribed regimes.

Complications / Failure of treatment

- Complication types
- Actions arising from complications
- Treatment failure (Y/N)

Analysis

The primary interest are the sub-group of children with acute SA / OM and no chronic comorbidities (simple cases). All analyses described below will therefore be carried out for this sub-group in the first instance. The other two sub-groups (chronic SA/OM and infections arising from previous orthopaedic surgery) will be analysed separately as a secondary analysis. See *Appendix A: Template Results Tables* for tables referred to in the following analysis plan.

Objective 1

- [1A] See Section 8.2 above for demography and definition of diagnosis groups. Numbers and percentages will be calculated and results tabulated separately for: demographics; diagnosis groups; presentation; history of orthopaedic surgery; medical history; and antibiotics prescribed prior to presentation. See Tables 1A-1,2,3,4,5,6 below
- [1B] The clinical time-line from first presentation through to diagnosis will be explored. Time to hospital referral, first imaging, surgery, radiological diagnosis, and initiation of IV antibiotics will all be summarised using appropriate descriptive statistics [see Table 1B-1].
- [1C] The number and percentage of cases undergoing different types of surgery prior to diagnosis will be reported [see Table 1C-1].
- [1D] The number and percentage of cases testing positive for at least one micro-organism, and each of 8 unique micro-organisms will be reported, split by centre type (Tertiary / Secondary). Any other micro-organisms detected will be categorised and reported as “Other”. Of cultures testing positive for *Staphylococcus aureus*, the number and percentage where PVL is tested for will be reported. The number and percentage of cases where a PCR test is also carried out will be calculated by centre type. [See Table 1D-1].

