Other

Infection History in the last 12
calendar months?

Pneumonia

Septicaemia

Pyelonephritis

Cellulitis / soft tissue infection

Meningitis

Osteoarticular infection

Abdominal sepsis

Varicella

Other

History of Trauma in the last
month?

Other Surgery in 12 months prior to
presentation?

Pre-presentation variables that affect drug choice, dosage and duration. (Simple cases only)

TABLE 1A-7

Antibiotic Medical History	N(%)	Route		Duration
		IV	Oral	> 1 week
Penicillin allergy		-	-	-

Antibiotics (1 month
pre-presentation)

Any

Flucloxacillin

Clindamycin

Cefuroxime

Ceftriaxone

Amoxicillin

Co-Amoxiclav

Rifampicin

Vancomycin

Fusidic Acid

Teicoplanin

Other

1B: The clinical time-line for diagnosis

TABLE 1B-1

Diagnostic and hospital stay Time-line (Days)	Appropriate Summary Statistics
From first presentation to:	
Hospital Referral	
1 st Imaging	
Pre-diagnosis surgery	
Radiological diagnosis	
Initiation of IV antibiotics	
(proxy for diagnosis of OM/SA)	

1C: Surgical procedures carried out post presentation and prior to diagnosis (before or on the same day as initiation of IV antibiotics).

TABLE 1C-1

Surgery types	Rate n (%)
Any	
Aspiration	
Incision and drainage	
Drill decompression	
Curettage/excision	
Arthrotomy	
Arthroscopy	
Amputation	

Debridement

Fasciotomy

Compartment decompression

Secondary closure

Skin graft

Other plastic surgery

1D: Summary of range of tests carried out and sensitivity of conventional microbiological tests. (Simple cases only)

TABLE 1D-1

N(%)
Children with at least one conventional test carried out
At least one micro-organism detected
Specific mirco-organisms detected by conventional testing:
Staphylococcus Aureus
PVL tested for?
Kingella Kingae
Streptococcus pyogenes
Pseudomonas
Group b Streptococcus
Salmonella
Candida
Tuberculosis
Other
PCR testing carried out

Types of sample used for conventional microbiological testing. (Simple cases only)

TABLE 1D-2

N(%)

Number of different
sample types taken

0

1

2

>2

Sample types. Children
that had at least one:

Pus (periosteal)

Bone biopsy

Pus/Wound swab

Joint aspirate

Other

1E: Blood-tests carried out at presentation. (Simple cases only)

TABLE 1E-1

Blood tests at presentation	N(%) with at least one measurement on day of presentation	Summary statistic for test results	% with elevated* results
Hb			
WCC			
N			
Plt			
CRP			
ESR			
CRP & ESR		-	-
CRP & not ESR		-	-
CRP _{max} occurring at presentation		-	-

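### Sub-objective 1D asks what proportion of centres use PCR and PVL testing, but the planned analysis reports only percentages of cases and of cultures

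*SAP*

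**What the plan says.** Under Study Objectives, the test-use part of sub-objective 1D sets out to "find the proportion of centres that are performing PCR tests", and the same sentence extends this to testing for PVL-producing *S. aureus*. The unit is the centre. The next sentence of the same sub-objective turns to the proportion of children testing positive, so the text treats centres and children as different units.

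Under Analysis, Objective 1, paragraph [1D] gives two test-use results. For PCR: "The number and percentage of cases where a PCR test is also carried out will be calculated by centre type". For PVL, among cultures positive for *S. aureus*: "the number and percentage where PVL is tested for will be reported".

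In Appendix A, Table 1D-1 is restricted to simple cases and headed N(%). Its first row is "Children with at least one conventional test carried out", and the PVL and PCR rows follow with no centre denominator.

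Elsewhere, centres are summarised only to check that they cover the areas of the country (Representativeness of cases accrued). On scale, Sample size calculations says: "It is estimated that at least 500 cases will be accrued by around 50 centres over a 6-12 month period".

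**The concern.** The objective and its analysis use different units. A percentage of cases weights each centre by the number of children it contributes. A percentage of cultures weights it by its number of *S. aureus*-positive cultures. Neither is a proportion of centres.

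The SAP's first aim is to assess clinical practice in secondary and tertiary care. Whether a test is used a little in many centres or heavily in a few is a different finding about practice, and the planned output cannot tell the two apart. An analyst who follows the plan will finish without the figure that 1D asks for. One who improvises it will have to invent the rules after seeing the data.

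**Working it through.** The SAP states no figure on this point, so there is none to reproduce. The check is a comparison of units, followed by an illustration of how loosely the planned figure constrains the wanted one.

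**Units side by side**

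| Test | Sub-objective 1D | Analysis [1D] | Table 1D-1 |
|---|---|---|---|
| PCR | centres | cases, by centre type | children (simple cases) |
| PVL | centres | *S. aureus*-positive cultures | row beneath *S. aureus*, no centre denominator |

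**What a case percentage says about centres**

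Inputs: N = 500 cases and C = 50 centres, from Sample size calculations, so m = 500/50 = 10 cases per centre on average. That every centre has exactly 10 is my assumption. Let p be the fraction of cases with PCR.

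- Fewest centres testing: each testing centre tests all its cases. Number = Np/m, share = p.
- Most centres testing: the tested cases are spread as widely as possible. Number = min(C, Np), share = min(1, pm).
- If every centre tests each case independently with the same probability p, the expected share with at least one test = 1 − (1 − p)^10.

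| p | Tested cases | Fewest centres | Most centres | Same rate everywhere |
|---|---|---|---|---|
| 10% | 50 | 5 (10%) | 50 (100%) | 1 − 0.9^10 = 65.1% |
| 20% | 100 | 10 (20%) | 50 (100%) | 1 − 0.8^10 = 89.3% |
| 30% | 150 | 15 (30%) | 50 (100%) | 1 − 0.7^10 = 97.2% |
| 50% | 250 | 25 (50%) | 50 (100%) | 1 − 0.5^10 = 99.9% |

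The shares depend on p and m but not on C. The same ranges therefore apply within the tertiary centres or within the secondary centres, and splitting by centre type does not recover the proportion of centres.

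**Volume dependence of a centre count**

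Counting centres with at least one test has its own weakness. At a true testing rate of 10%, a centre with 10 cases shows at least one test with probability 65.1%. A centre with 20 cases (the funded maximum of 1,000 spread over 50 centres) does so with probability 1 − 0.9^20 = 87.8%. A centre with 3 cases (an assumed small contributor) does so with probability 1 − 0.9^3 = 27.1%. The count therefore has to be read beside the number of cases per centre. For PVL the relevant number is the *S. aureus*-positive cases per centre, which is smaller.

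**The case against.** The best reply is that the PCR percentage is already planned by centre type, and this would expose the most obvious distortion. A reader might infer that a few busy tertiary centres could make PCR look widespread: for instance, if 10 of 50 centres supplied 300 of 500 cases and always used PCR while the rest never did, 300/500 = 60% of cases but only 10/50 = 20% of centres would be using it. The documents do not support that as the expected result. The caseload split is invented, and if the 10 users were the tertiary centres the planned output would read 100% tertiary against 0% secondary, which shows the concentration. This part of the objection stands. What remains is variation between centres of the same type, which the split cannot show. For PVL, moreover, the text does not clearly promise a split.

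A reader might also infer that the result would misstate how widely the tests are available. The SAP asks which centres perform them, and data from clinical notes show use, not availability, under either analysis.

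It can further be said that this is one clause of one sub-objective, that "This service evaluation is a descriptive study", and that no hypothesis test, sample size or treatment comparison depends on it. All true, and it limits the weight of the point. It does not supply the missing analysis.

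Finally, the copy of Table 1D-1 at hand has a single N(%) column although [1D] describes a split. I take the text as governing and draw nothing from the table layout.

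**Conclusion.** The point holds as a mismatch between a stated question and its analysis. Carried out as written, the plan leaves the centre-level part of 1D unanswered for both PCR and PVL, and the planned percentages do not determine it. This rests on the wording alone.

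The illustrative size, 30% of cases being compatible with 30% to 100% of centres, rests on the assumed equal 10 cases per centre. With unequal volumes the lower end can fall below 30%. No claim is made about the direction or size of any actual discrepancy, which needs the data.

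The change should be made, because it is cheap and lets the study answer its own question. No inferential conclusion is at risk.

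**What to change.** Add to [1D] and Table 1D-1, by centre type:

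- the number and percentage of centres with at least one PCR-tested case, out of centres with at least one case;
- the number and percentage of centres with at least one PVL test, out of centres with at least one *S. aureus*-positive case.

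State three rules with these rows. First, that a centre is counted as performing a test if it has at least one such test. Second, that the count runs over all recorded cases, since a centre that used the test only in a complex or implant case would be missed in a table of simple cases. Third, which centre is credited when a child is transferred, as transfers are among the data collected. Show the distribution of cases per centre, and of *S. aureus*-positive cases per centre, beside the rows. Keep the case-level and culture-level percentages as separate lines. Confidence intervals are optional in a descriptive study.

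The cost is a short definition and two extra rows. No new data should be needed, provided the database holds the centre for each case, as the planned split by centre type implies. If the centre-level question is no longer wanted, rewording 1D to cases and cultures would remove the inconsistency, at the price of dropping the question.

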- 2C:** Describe the combinations of blood-tests carried out immediately prior to oral switch and summarise the test results. Calculate the average CRP at oral switch as a proportion CRP_{max} . Summarise blood test results over time: from presentation through to last test.
- 2D:** Describe the surgical procedures carried out post diagnosis but prior to discharge, i.e. therapeutic procedures. How many children had only one procedure, two procedures or more than two?
- 2E:** Summarise the length of time spent in hospital: from hospitalisation to discharge.
- [2F]: Summarise imaging carried out after initiation of IV, split by site type and image type. For each imaging type, identify cases that had at least one image carried out.
- 2G:** Describe the antibiotic regimes prescribed at discharge (drug, dose, frequency and duration). As part of this – what percentage went home on IV as opposed to oral?
- 2H:** Were discharge antibiotic regimes adhered to? Percentages of treatments shortened or changed post discharge, split by who made the decision: parent, hospital or GP. Describe the main reasons for non-adherence or change of regime post discharge.
- 3A:** Describe rates of different types of complication, and cross-tabulate with types of action taken.
- 3B:** Describe rates of Treatment Failure (Yes/No) and Any Complications (Yes/No) for different antibiotic regimes types. Measure associations between regime types and the two outcomes: Treatment Failure; and Any Complications.
- 3C:** Describe rates of Treatment Failure (Yes/No) and Any Complications (Yes/No) for different surgery types carried out post presentation. Measure associations between surgery types undertaken and the two outcomes: Treatment Failure; and Any Complications.

Description of the study population

Representativeness of cases accrued

The participating centres will be summarised and checked that they broadly represent all areas of the country. The numbers of cases withdrawn will be recorded.

Sample characteristics and initial categorisation of types of cases

The demographics of the sample (age, gender, medical history) will be described using summary statistics. Based on past medical history, cases will be categorised into four groups:

1. Simple cases
2. Complex cases
3. Current presentation due to infected implant or infected surgery from past orthopaedic surgery. (Subset of complex cases)
4. Misdiagnosed

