Any children not falling into any of these categories will be excluded from the analysis.

Definitions

1. Simple cases

Children presenting with SA or OM for the first time, and with no chronic comorbidities. Specifically:

- No orthopaedic surgery 6 months prior to presentation on same limb/joint
- No chronic co-morbidities (sickle cell disease, known immunocompromise, indwelling central venous catheter or PICC, cystic fibrosis, or cerebral palsy).

2. Complex cases

Children presenting with SA or OM who already have a diagnosis of SA or OM and/or have chronic comorbidities, but who are not presenting because of an infected implant from previous orthopaedic surgery. Specifically:

- Not presenting because of an infected implant
- Any orthopaedic surgery in 6 months prior to presentation on same limb/joint
- Any chronic co-morbidities (sickle cell disease, known immunocompromise, indwelling central venous catheter or PICC, cystic fibrosis, or cerebral palsy).

3. Infected implants

Children presenting with SA or OM who already have a diagnosis of SA or OM and who are presenting because of an infected implant from previous orthopaedic surgery.

4. Incorrect diagnosis of SA/OM

Some children captured by the database were treated for SA/OM but were later found to have a different diagnosis.

Completeness of follow-up

Follow-up data are collected at a follow-up visit at around 3 months post discharge. The number lost to follow up will be reported and the reasons where known will be documented. Any deaths and their causes will be reported separately.

Study Outcomes

This study examines many measurements routinely made in the diagnosis, treatment, and aftercare of children with SA or OM. There are three areas of key interest: Diagnosis (Objective 1); Treatment (Objective 2); and Complications Arising and/or Treatment Failures (Objective 3). The key endpoints are:

Diagnosis:

- Bones and joints affected
- Time taken from first presentation to:
 1. Referral to hospital
 2. Having surgery
 3. Initiation of IV antibiotics [this time-point used also as a proxy for a diagnosis being made]
- Surgical procedures carried out prior to diagnosis
- Imaging types used (X-ray, CT scan, ultrasound, bone scan, MRI), and results obtained
- Diagnostic blood tests carried out (Hb, WBC, N, Plt, CRP, ESR) and their outcomes
- Microbiological tests carried out (presence of any of 8 named micro-organisms)

Antibiotic Treatment in and post hospital stay:

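### Definition 3 is narrower than the group it defines, so a first infection from an infected implant falls into the primary Simple group or into no group

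*SAP*

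**What the plan says.** All references are to the SAP.

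- **Group list** (Sample characteristics and initial categorisation of types of cases). Group 3 is "Current presentation due to infected implant or infected surgery from past orthopaedic surgery. (Subset of complex cases". It asks for no earlier SA/OM. The list is followed by the rule "Any children not falling into any of these categories will be excluded from the analysis".
- **Definition 1, Simple.** The lead sentence is "Children presenting with SA or OM for the first time, and with no chronic comorbidities. Specifically", followed by two criteria. One is "No orthopaedic surgery 6 months prior to presentation on same limb/joint" and the other is absence of five listed comorbidities. Neither mentions an implant or earlier SA/OM.
- **Definition 2, Complex.** The lead sentence rests on earlier SA/OM or comorbidity, in children "not presenting because of an infected implant". The criteria repeat the implant bar and add recent same-limb surgery and comorbidity. They do not say whether these last two are joined by and or by or.
- **Definition 3.** The group is limited to "Children presenting with SA or OM who already have a diagnosis of SA or OM and who are presenting because of an infected implant". Infected surgery, which is in the list, is not mentioned.
- **Analysis section.** Simple cases are analysed first. The rest are "The other two sub-groups (chronic SA/OM and infections arising from previous orthopaedic surgery".
- **Table 1A-2 (Appendix A).** The row for this group covers infected implant or surgery from earlier orthopaedic surgery. It sits apart from Complex and sets no condition on earlier SA/OM.

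**The concern.** Definition 3 adds an earlier-diagnosis condition that the three other descriptions of the group lack, and it omits surgery-related infection, which all three include. A child whose first bone or joint infection comes from an implant fails definition 3. Complex is closed to that child because of the implant. Simple is open, because it never asks about implants.

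Two things are at stake. The primary population is meant to be uncomplicated acute infection, yet it can contain implant infections. Other children with implant infection are recorded in the database and then left out of every analysis, although the SAP provides a separate secondary analysis for infections of that kind. Two analysts following the document could also build different primary populations.

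**Working it through.** The SAP gives no figure to reproduce here, and no sample-size or power quantity bears on the point. The check is logical.

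**Inputs.** Four yes/no attributes taken from definitions 1 to 3:
- P: earlier SA/OM diagnosis
- I: presenting because of an infected implant
- S: orthopaedic surgery on the same limb or joint within 6 months
- C: a listed comorbidity

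This gives 2 × 2 × 2 × 2 = 16 profiles. The misdiagnosed group is set aside because those children do not have SA/OM.

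**Main reading: lead sentences and criteria taken together.**
- Simple = not P, not S and not C: 2 profiles (I absent or present)
- Complex = not I, and at least one of P, S, C: 8 − 1 = 7 profiles
- Group 3 = P and I: 4 profiles

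The groups do not overlap. 2 + 7 + 4 = 13, so 16 − 13 = 3 profiles are unclassified. One of the 2 Simple profiles has an infected implant. Failures: 3 + 1 = 4 of 16, all of them first infections with an infected implant.

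**The four first-infection implant profiles (P absent, I present) under five readings of the definitions:**

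| S | C | Lead sentences only | Criteria only, or | Criteria only, and | Both required | Taken together |
|---|---|---|---|---|---|---|
| no | no | Simple | Simple | Simple | Simple | Simple |
| no | yes | none | none | none | none | none |
| yes | no | Simple | none | none | none | none |
| yes | yes | none | none | none | none | none |

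Here or/and is how the surgery and comorbidity criteria of Complex are joined. Both required means that a child must satisfy the lead sentence and the criteria (joined by or) of a group.

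**Unclassified profiles out of 16**, in the column order above: 2, 3, 7, 5, 3. No reading places every profile.

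**Recurrent infection** (P present; I, S and C absent):
- Simple under both criteria-only readings
- Complex under lead sentences only and under the main reading
- no group when both are required

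**With the wider description of group 3** (I now meaning infection of an implant or surgical site, whatever P is), in order: group 3 = 8 profiles, Complex = 7, Simple = 1. The total is 16, with none left over and none placed twice.

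**The case against.** The strongest defence is that the intent is plain. Three places describe group 3 widely enough to take every implant infection, and the exclusion rule directly follows the list, so its categories could be those of the list. That explains what was probably meant. It does not settle the matter, because the text headed Definitions is the only operational rule, it says something else, and nothing states which prevails.

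The defence does succeed against several stronger readings that a reader might infer:

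- **Recurrent infections enter the primary group.** This follows only if the criteria alone are the working rule. The lead sentence of Simple confines it to first presentations, and read with the criteria it keeps recurrences out.
- **A first infection after recent surgery, without an infected implant, is both Simple and Complex.** This arises only if lead sentence and criteria are treated as rival rules. Under the main reading it is Complex.
- **The subset label in the list misplaces children.** It conflicts with definition 2, but the Analysis section and Table 1A-2 both keep the group apart from Complex. The label alone moves no child.
- **Durations would be lengthened and failure rates raised.** The SAP gives no durations, failure rates or group frequencies, so neither direction nor size is supported.
- **Children are lost from the database.** They are lost from the analysis only; the Sample size section has all eligible cases recorded.

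The design also limits the consequence: "This service evaluation is a descriptive study", and no confirmatory test depends on the grouping.

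**Conclusion.** The point holds for first SA/OM from an infected implant. Under all five readings of the definitions, such a child is Simple if there was no recent same-limb surgery and no listed comorbidity, and fits no group if there is a comorbidity. With recent surgery alone, the child fits no group under four of the five readings. On the main reading 4 of 16 profiles fail.

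That count measures gaps in the logic and says nothing about how many children are affected, since the profiles are not equally common. The number affected, and the size and direction of any effect on results, cannot be derived from the SAP. The conclusion assumes that the Definitions text is the rule to be applied. If the wider description of group 3 governs, the four failures disappear. The primary population should not depend on that guess.

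**What to change.** Replace definitions 1 to 4 with one ordered rule that places each child once:

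1. Final diagnosis is not SA/OM: misdiagnosed.
2. Otherwise, infection of an implant or surgical site from earlier orthopaedic surgery, with or without earlier SA/OM: group 3.
3. Otherwise, any of earlier SA/OM, orthopaedic surgery on the same limb or joint within 6 months, or a listed comorbidity: Complex.
4. Otherwise, with all these items known to be absent: Simple.

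Three additions are needed:

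- **Look-back.** State how far back earlier SA/OM counts. Table 1A-6 covers osteoarticular infection only over the previous 12 calendar months, so either adopt that limit openly or confirm that older history is recorded.
- **Unknown status.** Table 1A-5 allows for comorbidities that were not tested or are unknown. Report children with an unknown defining item as a separate unclassified count, in place of the present exclusion sentence. They should neither default to Simple nor disappear unreported.
- **Wording.** Delete the subset label and use the same group descriptions in the Analysis section and the Table 1A-2 footnotes.

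The cost is SAP wording and one derived variable. Further data would be needed only if the chosen look-back exceeds what was recorded.
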